### 6.2. STATISTICAL ANALYSIS PLAN

The primary analysis will compare number of days of hospitalization from randomization to discharge, death, transfer or 48 weeks PMA, whichever occurs first between the intervention and control groups using median regression controlling for study center and GA group (the two stratification factors for this trial). Likewise, the treatment effect for the secondary outcomes (number of days to physiologic maturity after randomization, number of readmissions and number of sick visits) will be compared using either median regression or a Poisson regression model controlling for study center and GA group.

Secondary analyses will evaluate whether other models better fit the distributions for these outcomes (for example, survival analysis models for the primary outcome and negative binomial or log linear models for the secondary outcomes).

We will examine treatment heterogeneity for the primary outcome by adding interaction terms between treatment and study center, as well as treatment and GA group. If any of these interaction terms are close to statistical significance ( $p<0.1$ ), for treatment heterogeneity by study center, we will attempt to identify centers where the treatment effect may be different (although the statistical power available to conduct such analyses will be fairly limited). If there is

indication of treatment heterogeneity by GA group, we will conduct stratified analyses by GA group to quantify the treatment effect separately by GA group.

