#### Inclusion Criteria:

- 1.  $33^{0/7}$   $35^{6/7}$  weeks PMA at the time of randomization
- 2. Receiving caffeine with plan to discontinue treatment or just discontinued caffeine treatment
- 3. Receiving full feeds (defined by a volume of  $\geq$ 120 ml/kg/day) by oral and/or tube feeding
- 4. Ability to start study medication within 72 hours after stopping caffeine

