#### 4.4 Study Arm Assignment and Randomization

When the attending neonatologist has discontinued clinical caffeine on an eligible and consented infant that is  $33^{0/7}$  -  $35^{6/7}$  weeks PMA, the infant can be randomized if it is possible to start study medication within 72 hours after stopping caffeine.

Infants will be randomized 1:1 using a stratified randomly permutated block design with a centralized procedure. Infants will be stratified by study center into two GA groups; infants born at 29 to 30 6/7 weeks GA and 31 to 33 6/7 weeks GA. Randomization will occur through the Data Coordinating Center (DCC) of RTI International (Research Triangle Park, North Carolina). Treatment allocation will be revealed only to the research pharmacy staff, who will prepare either caffeine citrate at 10 mg/kg (base of 5 mg/kg) or an equivalent volume of placebo to be administered once a day. The dosage will be based on the weight closest to randomization and then adjusted weekly for weight. Because both caffeine and placebo are colorless, they are indistinguishable and, therefore, blinding will be accomplished for all care providers and research staff. The oral delivery should begin as soon as clinically possible.

Randomization of twins and higher order multiples (when eligible) will be done independently.

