## 7.2 Adjustments for Covariates

Indicator variables for the study stratification of site and gestational age will be included as covariates in most efficacy analyses performed for this study. Additionally, demographic and baseline characteristics for subjects will be compared between study arms using analysis of covariance techniques for continuous measures, Mantel-Haenszel mean score test using standardized mid-rank scores for ordinal measures, and Cochran Mantel-Haenszel chi-square tests for general association for categorical measures. If sample sizes allow, these analyses will control for the study stratification factors. If these analyses suggest that substantial differences exist among arms, the use as covariates of these parameters on which the arms differ will be explored in exploratory analyses of the efficacy data.

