## **Interim Efficacy Monitoring**

Statistical interim efficacy monitoring will be conducted by the DCC after 25%, 50% and 75% of the babies enrolled into the trial complete eight-week follow up period. At each of these interim looks, the primary outcome will be compared by (blinded) treatment group using the methods outlined in Section 9. O'Brien Fleming stopping bounds for efficacy will be used to preserve an overall Type-I error rate of 0.05 for the primary outcome. Thus, stopping bounds for efficacy will be established if p  $< 5 \times 10^{-5}$  at 25%, p < 0.004 at 50% and p < 0.018 at 75% of interim data accrual. In the event that these stopping bounds are reached, the DSMC may recommend termination of the trial for efficacy. In addition to the primary outcome, secondary efficacy outcomes collected in this trial will also be examined by treatment group.

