## 8.4 Demographic and Baseline Characteristics

Demographic and baseline clinical characteristics for the study participants will be summarized by study arm using the general analysis rules describe above. Variables of interest include mother demographics, gender, gestational age, race and ethnicity, and in-hospital clinical outcomes at the time of birth.

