## 9.2 Efficacy Variables

Primary and secondary efficacy variables are described in the table below.

| Variable                               | Type  | Definition   |  |
|--|-------|--|--|
| Primary Outcome                        |       |  |  |
| Number of days of hospitalization      | Count | The number of days between randomization and hospital discharge. This outcome is censored at 48 weeks PMA and at time of transfer or death   |  |
| Secondary Outcomes                     |       |  |  |
| Number of days to physiologic maturity | Count | Physiologic maturity is defined:  i. Temperature: out of the incubator for at least 48 hours with normal body temperature  ii. Feeding: oral feeding at a volume of at least 140 ml/kg for 48 hours or growing on less than 140 ml/kg/day for at least 48 hours  iii. Respiratory: apnea-free for at least 5 consecutive days  This outcome is censored at 48 weeks PMA. |  |

| Variable  | Type       | Definition  |
|---|------------|---|
| Number of days to physiologic maturity - Temperature                        | Count      | Physiologic maturity is defined:  i. Temperature: out of the incubator for at least 48 hours with normal body temperature  This outcome is censored at 48 weeks PMA.  |
| Number of days to
physiologic maturity –
Feeding                      | Count      | Physiologic maturity is defined:  i. Feeding: oral feeding at a volume of at least 140 ml/kg for 48 hours or growing on less than 140 ml/kg/day for at least 48 hours  This outcome is censored at 48 weeks PMA.            |
| Number of days to
physiologic maturity -
Respiratory                  | Count      | Physiologic maturity is defined:  i. Respiratory: apnea-free for at least 5 consecutive days This outcome is censored at 48 weeks PMA.  |
| Post-menstrual age at discharge   | Continuous | The post-menstrual age of the infant at discharge censored at 48 weeks PMA and at time of transfer or death   |
| Number of all-cause
readmissions within first 4
weeks post-discharge  | Count      | Number of hospital readmissions including apneic events and apparent life-threatening events during first 4 weeks following hospital discharge. The outcome is censored at 48 weeks PMA.                                    |

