## 9.3 Primary Analysis Methods

For the primary analysis, the number of days of hospitalization between randomization and discharge will be compared between the caffeine citrate and placebo groups using either median or robust Poisson regression models. The model will include a fixed effect for treatment group. The model will also be adjusted for the design effect of stratification by site and gestational age. Estimates, p-values and 95% confidence intervals will be presented for treatment group comparisons. In an intent-to-treat fashion, all data will be included in the primary model based on their randomized treatment, regardless of the treatment administered to the patient. If there are important baseline characteristics that differ between randomized treatment groups by chance, additional sensitivity analyses may be conducted to evaluate the impact of those imbalances.

We will examine treatment heterogeneity for the primary outcome by adding interaction terms between treatment and study center, as well as treatment and gestational age group, and following NIH guidelines, treatment and sex. If any of these interaction terms are close to statistical significance (p<0.1), for treatment heterogeneity by study center, we will attempt to identify centers where the treatment effect may be different (although the statistical power available to conduct such analyses will be fairly limited). If there is indication of treatment heterogeneity by GA group and/or sex, we will conduct stratified analyses by GA group and/or sex to quantify the treatment effect separately by GA group/sex.

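### The primary model leaves out post-menstrual age at randomization, a baseline part of the outcome that may span 21 days, and so may give up precision for no saving.

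*SAP*

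**What the plan says.** SAP 9.2 defines the primary outcome as the days between randomization and hospital discharge, censored at 48 weeks PMA, transfer or death. SAP 9.3 includes a treatment effect and adds: "The model will also be adjusted for the design effect of stratification by site and gestational age". SAP 7.2 agrees: "Indicator variables for the study stratification of site and gestational age will be included as covariates in most efficacy analyses performed for this study". Protocol 6.2 specifies median regression "controlling for study center and GA group (the two stratification factors for this trial").

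The gestational-age factor is age at birth in two bands: "infants born at 29 to 30 6/7 weeks GA and 31 to 33 6/7 weeks GA" (SAP 4.4). Age at entry appears only as an eligibility window. SAP 4.3 requires 33 0/7 to 35 6/7 "weeks PMA at the time of randomization".

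For the baseline table, SAP 8.4 says: "Variables of interest include mother demographics, gender, gestational age, race and ethnicity, and in-hospital clinical outcomes at the time of birth". PMA at randomization is not named.

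Other covariates come in only after an imbalance is seen, as exploratory analyses (SAP 7.2) or as optional sensitivity analyses (SAP 9.3). SAP 9.5 lists no exploratory methods. A related secondary outcome is defined in SAP 9.2 as "The post-menstrual age of the infant at discharge censored at 48 weeks PMA and at time of transfer or death", but SAP 7.7 makes secondary p-values descriptive.

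**The concern.** PMA at randomization is subtracted, by definition, in forming the outcome. It must be known for every infant to establish eligibility. Neither gestational-age band fixes it, because infants from either band may enter across the window. If infants tend to go home at a similar PMA, those who enter later will stay fewer days. Part of the spread in length of stay would then be explained by a value known before treatment starts.

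The protocol makes a relation plausible. It describes respiratory maturation with rising PMA (3.3) and average discharge between 35 and 37 weeks (3.4). It also gives a reason for a weaker one: entry is triggered by stopping caffeine, and Protocol 4.5.1 says most neonatologists then observe infants in hospital for at least five days. That would flatten the relation between entry PMA and stay.

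What is at stake is precision in the primary comparison. Chance differences in entry PMA between arms would also pass unadjusted into the primary estimate.

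**Working it through.** **Inputs from the documents.** Effect 2 days (14 to 12); two-sided significance 0.05; attrition 5%; 439 per group (878) at 80% power; 587 per group (1174) at 90% (SAP 6). The entry window has 21 possible days (SAP 4.3).

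**Inputs assumed.** The documents do not give the SD of stay, the spread of entry PMA, or the slope (days of stay saved per day of later entry).

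**Step 1: SD implied by the plan's sample size.** On a mean-difference scale, SD = 2 × √(n/2) / (z for significance + z for power).
- 878: n = 439 × 0.95 ≈ 417 per arm, so SD = 2 × √208.5 / (1.960 + 0.842) = 10.31 days.
- 1174: n = 587 × 0.95 ≈ 558 per arm, so SD = 2 × √278.8 / (1.960 + 1.282) = 10.30 days.

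The two rows agree. The SD is back-solved, so this is a consistency check and not independent confirmation of 878.

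**Step 2: spread of entry PMA.** If uniform over 21 days, SD = 21/√12 = 6.06 (variance 36.75). If clustered, SD is taken as 4 (variance 16).

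**Step 3: variance explained and power.** R² = slope² × entry variance / 10.31². Power = Φ(2 / (10.31 × √(1 − R²) × √(2/417)) − 1.96). The equivalent unadjusted total is 878/(1 − R²). Ranges run from entry SD 4 to 6.06. The last column halves R², in case center and GA group already absorb half of it.

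| Slope | R² | Power at 878 | Equivalent total | Power, R² halved |
|---|---|---|---|---|
| 0 | 0 | 80% | 878 | 80% |
| 0.3 | 1.4-3.1% | 80.5-81.2% | 890-906 | 80.3-80.6% |
| 0.5 | 3.8-8.6% | 81.5-83.4% | 912-961 | 80.7-81.7% |
| 0.8 | 9.6-22.1% | 83.8-88.8% | 972-1128 | 81.9-84.4% |
| 1.0 | 15.1-34.6% | 86.0-93.4% | 1034-1342 | 83.0-86.9% |

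Slope 1.0 means that discharge PMA does not depend on entry PMA at all. It is an upper extreme.

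**Step 4: the larger target.** With 558 per arm, the same formula gives 90% unadjusted, 90.3-90.8% at slope 0.3 and 91.0-92.3% at slope 0.5.

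**Step 5: median regression.** The planned model is not a comparison of means, so it was simulated with 834 infants and total SD 10.3.
- Without center or GA terms (normal or gamma residuals, 1,200 replicates per setting), adjusting changed power by −0.6 to 0.6 points at slope 0. It added 2.1 to 3.6 at 0.5, 1.9 to 12.9 at 0.8 and 8.0 to 20.9 at 1.0.
- With center and GA terms, there was no loss of precision at slope 0. The ratio of adjusted to unadjusted standard error was about 0.95-0.98 at slope 0.5 and 0.73-0.94 at slope 1.0.

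**Step 6: chance imbalance.** The 95% range for the difference in mean entry PMA between arms is ±1.96 × entry SD × √(2/417). This is ±0.54 days (SD 4) to ±0.82 days (SD 6.06). At slope 0.5 it shifts the unadjusted estimate by up to 0.27 to 0.41 days, or 14-20% of the 2-day target.

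**The case against.** A model adjusted for the stratification factors is complete and valid, and the gain from one more covariate is unknown and may be nil. Every figure rests on an assumed slope and spread and on an SD back-solved for means, although the plan compares medians. At slopes of 0.3 to 0.5 the gain at 878 is only about 0.5 to 3 points. The 878 is a minimum, and at 1174 the gain for slopes up to 0.5 is about 0 to 2 points. All of this stands and limits the weight of the point.

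The simulated gains also need care. Residual shape and noise matter at moderate slopes. One median-regression check with skewed residuals started from 66-69% unadjusted power, so the gains cannot simply be added to 80%. The objection that center and GA terms were omitted is met by the simulation that included them.

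It can be said that the plan already covers the issue through PMA at discharge and the imbalance analyses. PMA at discharge is the slope-1 version of the comparison, but it is secondary and descriptive. Adjustment triggered by observed imbalance does nothing for the precision of the primary test. The list in SAP 8.4 is not closed, so entry PMA might still be tabulated; the plan just does not ensure it.

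The SAP is marked final in December 2022 and drug expiry is given as about August 2023, so interim looks may already have taken place. The documents do not say. That is a reason for a masked, dated decision, and it does not remove the case for adjusting.

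**Conclusion.** The concern holds as a loss of efficiency. Both documents omit PMA at randomization from the primary model, although it is a component of the outcome and is known for every infant. The randomized comparison stays unbiased, type I error is unaffected and 878 stands.

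The benefit is uncertain. Under the assumptions above, power at 878 rises from 80% to about 82-83% at slope 0.5, or 81-82% if center and GA group already absorb half of the explained variance. The extreme is 86-93% at slope 1.0, and there is no gain at slope 0. The simulations found no material loss when the covariate was unrelated to stay. The change is worth making but is not essential to validity. Confidence in its size is medium at best.

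**What to change.** Before unblinding, prespecify continuous PMA at randomization, in days, as a covariate alongside center and GA group in SAP 7.2 and 9.3 and Protocol 6.2. State that the median-regression treatment coefficient is then a median difference conditional on that covariate. Keep the stratification-only model as a sensitivity analysis, name PMA at randomization in the SAP 8.4 baseline table, and record the change in SAP 13.

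Use the same model at any interim look still to come, because SAP 7.4 says "the primary outcome will be compared by (blinded) treatment group using the methods outlined in Section 9". The interim programs must match.

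SAP 4.6 lists the study statistician among the unblinded staff, so masked investigators should make and date the decision.

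The cost is one degree of freedom, the text edits and the program changes. It needs no new data and places no burden on infants or families.

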## 9.4 Secondary Analysis Methods

Secondary outcomes will be compared between treatment groups using models similar to the primary outcome for continuous measures and analogous generalized linear models for categorical outcomes.

Additionally, secondary analyses will evaluate whether other models better fit the distributions for both the primary and secondary outcomes (for example, survival analysis models for the primary outcome and negative binomial or log linear models for suitable secondary outcomes).

## 9.5 Exploratory Analysis Methods

Not Applicable.

#### 10 SAFETY ANALYSES

## 10.1 Overview of Safety Analysis Methods

All safety analyses will be performed using all participants who were randomized and evaluated based on the treatment they received. The frequency of toxicities potentially attributable to study treatment will be determined. Treatment and resolution of all safety endpoints will also be documented. Treatment groups will be compared for incidence of events with a chi-squared or Fisher's exact test, and incidence density (events per person-months of exposure) will be calculated.

## 10.2 Safety Variables

Safety outcome variables are described in the table below.

| Variable   | Туре                       | Definition  |
|--|----------------------------|---|
| Safety Outcomes  |                            |   |
| Weight gain from randomization until status  | Continuous/
Categorical | Change in weight between randomization and in-hospital status. Outcome is censored at 48 weeks PMA and time of transfer or death. May also be assessed using percentiles.   |
| Number of days after
randomization until status
that infant had at least two
consecutive heart rates >200
documented at least 3 hours
apart | Count                      | Number of days between randomization and status with at least 2 consecutive heart rates > 200 bpm at least 3 hours apart. Outcome excludes when infant was crying.  |
| Treatment for high blood pressure initiated after randomization until status   | Categorical                | Presence of treatment for high blood pressure that was started between randomization and status.  |
| Number of episodes between randomization and status that infant was placed NPO for ≥ 24 hours  | Count                      | Number of days between randomization and status in which infant was placed NPO for at least 24 hours  |
| Use of anti-reflux medications between randomization and status  | Categorical                | Presence of use of anti-reflux medication that were started between randomization and status.   |
| Number of days of
significant apnea/bradycardia
between randomization and
status  | Count                      | Number of days between randomization and status with infant showing significant apnea/bradycardia. Significant apnea/bradycardia documented by infant receiving open label caffeine, doxapram, other methylxanthines, CPAP or ventilatory support for apnea/bradycardia |

| Variable  | Type        | Definition   |
|---|-------------|--|
| Presence of documented and treated arrhythmias between randomization and status | Categorical | Presence of treated arrhythmias between randomization and status. Outcome excludes arrhythmias due to tachycardia or bradycardia     |
| Onset of documented seizures between randomization and status                   | Categorical | Presence of documented seizures between randomization and status. Documented seizures are defined by treating with anti-convulsants. |

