### 4.5.2. Risks

Neofax, a pharmaceutical reference source, includes side effects of caffeine citrate such as vomiting and restlessness, as well as functional cardiac symptoms, all based on low level of evidence studies. In two randomized-controlled trials, the frequency of side effects between infants receiving caffeine and those in the placebo group did not differ. Data on these measures are not collected usually in clinical care or trials so we will not collect them.

In the largest caffeine trial to date, the Caffeine for Apnea (CAP) trial, decreased weight gain was reported in the caffeine group as compared to the placebo group in the first days of treatment. However, weight gain during the hospitalization did not differ between caffeine and placebo group infants. In a recent large, randomized controlled trial of high-dose (caffeine

citrate 20 mg/kg, twice the dose planned for this trial) versus normal-dose caffeine (caffeine citrate 5 mg/kg), tachycardia was more frequent but still relatively uncommon occurring in 4% in the high-dose group. There was no difference in any other adverse effects between groups including feeding intolerance despite the use of doses much higher than those that will be used in the current trial. Serious toxicity has been noted in patients who have inappropriately received overdoses of caffeine with blood levels exceeding 50 mg/L but are rare with correct dosing. The most recent Cochrane meta-analysis did not include an analysis of side effects related to the use of methylxanthines.

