## 3.2.2 Secondary Outcomes

- 1. The number of days to physiologic maturity after randomization up to 48 wks PMA. Physiologic maturity will be defined as follows:
  - a) Temperature: out of the incubator for at least 48 hours with normal body temperature
  - b) Feeding: oral feeding at a volume of at least 140 ml/kg/day or growing on less than 140 ml/kg/day for at least 48 hours
  - c) Respiratory: apnea-free for at least 5 consecutive days
- 2. Post menstrual age at discharge up to 48 wks PMA, censoring at time of transfer or death (status).
- 3. The number of all cause readmissions, including apneic events and apparent life-threatening events (ALTE), to the hospital within the first four weeks, second four weeks, and first eight weeks combined after discharge from the hospital by 48 wks PMA.
- 4. The number of all cause sick visits to urgent care, emergency room or health care provider office within the first four weeks, second four weeks, and first eight weeks combined after discharge from the hospital by 48 wks PMA.
- 5. Safety outcome measures pre-hospital discharge:
  - a) Weight gain from randomization until status (discharge up to 48 wks PMA, with censoring at time of transfer or death). The weight gain may also be assessed using percentiles including birthweight percentiles.
  - b) The number of days after randomization until status that infant had at least two consecutive heart rates >200 documented at least 3 hours apart (when infant not crying).
  - c) Treatment for high blood pressure initiated after randomization until status.
  - d) The number of episodes between randomization and status that infant was placed NPO for ≥ 24 hours.
  - e) The use of anti-reflux medications started between randomization and status
  - f) The number of days that significant apnea/bradycardia, as defined by documentation of infant receiving any of the following between randomization and status: open label caffeine, other methylxanthines, doxapram, continuous positive airway pressure (CPAP) or ventilatory support for apnea/bradycardia.
  - g) The presence of documented and treated arrhythmias between randomization and status, not due to tachycardia or bradycardia.

h) The onset of documented seizures, as defined by treating with anti-convulsants, between randomization and status.

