#### **6 SAMPLE SIZE DETERMINATION**

To obtain a two-day difference in the primary outcome of days from randomization to discharge, from 14 days to 12 days, with a power set at 90%, a significance of 0.05, and a 5% attrition, the trial would require 587 infants per group (intervention and placebo) for a total of 1174 infants, assuming a two-tailed, non-parametric test comparing median LOS in the two groups. With a power set at 80%, under the same assumptions and significance, the trial would require 439 infants per group for a total of 878 infants. The minimum required sample size for this trial will be 878 (439 in each treatment group), but enrollment will continue until either the available supply of study drug is exhausted or expires in approximately August 2023 (accounting for full in-hospital and post-discharge follow-up), whichever comes first.

There are approximately 3000 infants born between 290/7 and 33 6/7 weeks gestation per year in the NRN. A review of 100 infants in the NICU at one of the largest centers in the NRN showed that 37% of infants within this cohort were treated with a methylxanthine. This is similar to NRN data showing that approximately 1000 (one-third) of infants receive caffeine therapy. The following table shows scenarios for approximate time to completion of the trial as a function of consent rate and NICHD center involvement:

| Consent Rate (%) | Time to Completion (mo), all sites | Time to Completion (mo), half sites |
|------------------|------------------------------------|-------------------------------------|
| 50               | 24                                 | 48                                  |
| 60               | 20                                 | 40                                  |
| 70               | 18                                 | 36                                  |
| 80               | 15                                 | 30                                  |

| Effect Size (days) | Significance | Power (%) | Attrition (%) | Sample Size |
|--------------------|--------------|-----------|---------------|-------------|
| 14 to 10           | 0.05         | 80        | 5             | 226         |
| 14 to 10           | 0.05         | 90        | 5             | 302         |
| 14 to 12           | 0.05         | 80        | 5             | 878         |
| 14 to 12           | 0.05         | 90        | 5             | 1174        |

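### Weight gain is total change from randomization to status, so if caffeine shortens the stay, equal daily growth will still show as lower weight gain on caffeine

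*SAP*

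**What the plan says.** The SAP 10.2 table defines weight gain as "Change in weight between randomization and in-hospital status". SAP 3.2.2 and Protocol 4.2 use the same window and explain status: discharge, no later than 48 weeks PMA, or censoring at transfer or death. The only alternative offered is percentiles. SAP 10.2 says "May also be assessed using percentiles", and SAP 3.2.2 says "The weight gain may also be assessed using percentiles including birthweight percentiles". Neither section names a reference, an age at which the percentile is read, or a method of comparison.

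The primary outcome runs over that same interval. Protocol 3.1.1 hypothesises that caffeine shortens it, and SAP 6 sizes the trial for a change "from 14 days to 12 days".

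On methods, SAP 9.4 states "Secondary outcomes will be compared between treatment groups using models similar to the primary outcome for continuous measures". Those models adjust for site and gestational age. SAP 10.1 covers safety outcomes with tests of event incidence and adds that "incidence density (events per person-months of exposure) will be calculated". SAP 7.7 makes all safety p-values descriptive.

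On prior evidence, Protocol 4.5.2 reports from the largest earlier trial that "decreased weight gain was reported in the caffeine group as compared to the placebo group in the first days of treatment", but also that "weight gain during the hospitalization did not differ between caffeine and placebo group infants".

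**The concern.** Total weight gained is daily growth multiplied by days observed. Here the days observed run to discharge, and the treatment is meant to change when discharge happens. If the primary hypothesis is true, the arms are compared over intervals of different length. The arm that goes home sooner has less time to gain weight, so a lower total could mean slower growth, earlier discharge, or both. The variable cannot tell these apart.

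The error can run the other way. If caffeine infants stayed longer, the extra days could make up for slower growth and hide it. If stays do not differ, there is no artefact.

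Weight is the first safety measure listed in SAP 3.2.2 and SAP 10.2. It is also among the Protocol 6.3.1 safety data, which SAP 7.4 says will be examined by arm at the interim looks. The protocol's own evidence suggests at most an early, transient slowing. A trial that met its primary aim could therefore report reduced weight gain on caffeine as a safety finding when daily growth was the same.

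**Working it through.** The documents give no expected value, SD or margin for weight gain, so there is no stated figure to reproduce. The check asks what the planned measure returns when daily growth is identical in both arms.

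**Inputs from the documents**
- Median stay after randomization of 14 days on placebo and 12 on caffeine; alternative scenario 14 to 10 (SAP 6).
- Weight measure: total change, randomization to status (SAP 10.2).

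**Assumed inputs, not in the documents**
- Daily growth of 20 to 40 g/day, or 10 to 20 g/kg/day.
- Weight at randomization of 1500 to 2100 g.
- Weighing error of 30 g.

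**Step 1. Relative shortfall.** With equal daily growth *g* and stays shortened proportionally, total gain is *g* × days. The ratio of arms is (caffeine days)/(placebo days), and *g* cancels.

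| Stay, placebo vs caffeine | Shortfall on caffeine | Grams at 20 / 30 / 40 g/day |
|---|---|---|
| 14 vs 14 | 0 | 0 / 0 / 0 |
| 14 vs 13 | 1 - 13/14 = 7.1% | 20 / 30 / 40 |
| 14 vs 12 | 1 - 12/14 = 14.3% | 40 / 60 / 80 |
| 14 vs 10 | 1 - 10/14 = 28.6% | 80 / 120 / 160 |

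**Step 2. Exponential growth.** If growth is constant in g/kg/day at rate *k*, the shortfall for 12 versus 14 days is 1 - (e^(12k/1000) - 1)/(e^(14k/1000) - 1).
- *k* = 10: 1 - 0.1275/0.1503 = 15.2%.
- *k* = 20: 1 - 0.2712/0.3231 = 16.1%.

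The result does not depend much on the growth model.

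**Step 3. Masking in the other direction.** Placebo: 14 days × 30 g/day = 420 g. Caffeine: 16 days × 26.25 g/day = 420 g. A stay two days longer would exactly hide growth that is 1 - 26.25/30 = 12.5% slower.

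**Step 4. Does velocity remove the artefact?** Velocity = 1000 × ln(weight at status / weight at randomization) / days. Starting at 1800 g and growing linearly at 30 g/day:
- 14 days: 1000 × ln(2220/1800)/14 = 14.98 g/kg/day.
- 12 days: 1000 × ln(2160/1800)/12 = 15.19 g/kg/day.
- Ratio 15.19/14.98 = 1.014.

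Over 1500 to 2100 g and 20 to 40 g/day the ratio lies between 1.009 and 1.021. A difference of about 14% becomes 1 to 2%. Under growth that is constant in g/kg/day it is zero.

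**Step 5. Cost in precision.** A 30 g weighing error is 30/2 = 15 g/day over 2 days but 30/14 = 2.1 g/day over 14 days. Velocity is noisy for short stays.

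**Step 6. Would the artefact be visible at the planned size?** A simulation used 417 infants per arm (439 × 0.95), lognormal stays with medians 14 and 12 and log-SD 0.5 to 0.7, and identical daily growth (mean 30, SD 8 g/day). Total gain differed at nominal p < 0.05 by rank test in 84% to 97% of runs, against 4% to 5% for g/day. These percentages depend on the assumed distributions. In the same runs the rank test on stay itself had 90% to 99% power, above the 80% for which 878 infants were planned, so they are probably on the high side. The simulation tested g/day, not the logarithmic formula of Step 4.

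**The case against.** The arithmetic is not in dispute; the case against concerns its importance.

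- **Later weights are planned.** Protocol 6.3.1 also intends to monitor weight at well-child visits, around one and/or four weeks after discharge. Measured to four weeks after discharge, the two-day difference would matter less: 1 - (12 + 28)/(14 + 28) = 4.8%. But the SAP 10.2 variable stops at status and does not use those weights.
- **Length of stay is reported alongside.** The interim reports show the primary outcome and the safety outcomes by group, so a reader would see the shorter stay. That gives context, but no planned analysis joins the two.
- **The likely error is a false alarm.** Under the trial's hypothesis the artefact makes caffeine look worse, and masking needs a longer stay on caffeine. The formal safety bounds do not use weight, and safety p-values are descriptive. This stands, and it limits the harm to a misleading estimate.
- **Percentiles are already named.** A weight-for-PMA percentile would remove much of the artefact. It is optional, however, and nothing says which percentile is meant. A birthweight percentile alone does not describe growth after randomization.
- **The governing model is unclear.** Weight is listed as a secondary outcome but defined in the safety section, so either SAP 9.4 or 10.1 might apply. Neither adjusts for days observed, and incidence density cannot be applied to grams.
- **Velocity has its own limits.** It is noisy for short stays, and discharge depends partly on feeding and growth, so it is not guaranteed to be free of bias. This stands and is the reason for a stated short-stay rule.

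**Conclusion.** The concern holds. As defined, the weight-gain measure mixes growth with length of stay. If caffeine shortens the stay from 14 to 12 days and daily growth is the same, the caffeine arm will show about 14% less weight gain (7% for one day, 29% for four). The percentage assumes equal linear growth and proportionally shorter stays, but no particular daily rate. The gram figures, 40 to 80 g for two days, rest on an assumed 20 to 40 g/day.

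The artefact is conditional on a difference in stay, but that difference is the trial's primary hypothesis. No formal decision depends on this variable. The consequence is a safety estimate that would mislead if the trial succeeds. The primary result is unaffected, and the correction is cheap.

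**What to change.** In SAP 10.2:

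- Make the main weight measure growth velocity in g/kg/day: 1000 × ln(weight at status / weight at randomization) / days between the two weights. Change in weight-for-PMA z-score from a named reference is an acceptable alternative and would also define the percentile option.
- Compare arms by median regression adjusted for site and GA group, and say that this model governs weight.
- State a rule for very short stays. For example, include every infant with at least one day between weights, and report by arm how many had fewer than three. Excluding short stays would select on the primary outcome. Median regression limits the influence of the noisiest values.
- Keep total change as a descriptive summary, shown beside days from randomization to status in each arm.

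The cost is essentially SAP wording. Protocol 5.2.3 and SAP 4.8 already collect weights at randomization and status and the date of status. One detail needs checking: the listed data do not include the date of each weighing. If the forms do not record it, the SAP should say that the randomization and status dates define the interval.
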